2.0	09 Nov 2021	PPD	
 • Minor editorial changes • Signature page adapted to new electronic signature process • Major PD -> Key PD • Section 3: Document versions updated • Glossary: Infusion terminology clarified. • Section 4.6/ 5: Interim Analysis: Changed timing and purpose (change from CSP), specification added • Section 6: SAF-IgPro10 and SAF-IgPro20 added • Section 6: PP-IgPro10 and PP-IgPro20 added, PK analysis set removed • Section 7.4 (COVID-19 Impact) added • Section 8.1.2: Imputation rules for Concomitant Medication changed • Section 8.2.3: Duration of AE and Time to Onset from last infusion is expressed in minutes • Section 8.2.3: Duration since SSc history event added • Section 8.2.9 and 10.1: CCI response added • Section 8.2.13: 'Other aids' can now be assigned to an activity • Section 8.2.13: Screenshots for CCI CCI added • Section 8.3.2: Categorization of Concomitant Medications takes now start and end times into account • Section 8.4.2: Deleted "two consecutive visits" for vital signs and CCI • Section 9: Clarification of handling of re-screened subjects • Section 9.1: List of parameters re-arranged • Section 9.3: Auto-antibodies at baseline added • Section 9.3/9.4: Summaries for background therapy/ immunosuppressants at baseline added

Ver- sion	Effective Date	Author of Modification	Reason for Change
			
 • Section 9.4: Changed categories of Prior/ Concomitant Medications • Section 9.4: Summary added for concomitant medications used to treat COVID-19 associated adverse events • Section 10.1: Clarify that bootstrap method will be used to derive confidence intervals. • Section 11.1: Addition of parameters for IgPro10 • Section 11.1: Separated "Duration" into "Duration of infusion" and "Duration of Treatment" to avoid confusion • Section 11.2: Replaced "Treatment-emergent AESIs by Category, PT and grade" by "... maximum grade (without number of events)" • Section 11.2: "Injection site reaction" added to the list of HLTs to find "Infusion site reactions" • Section 11.2: Clarification of calculations for ISR • Section 11.2: Listing of TEAEs leading to permanent discontinuation of IP added • Section 11.2: Due to expected low number of events: no summary of SAE and TEAEs leading to permanent discontinuation of IP by treatment sequence • Section 12: PK analysis will be done on SAF; sensitivity analysis added for bioavailability • Section 12.2, Table 9: Reference interval for Tmax/Cmax ends at AH10/BH21 • Section 12.3: "baseline-corrected AUC " is used for bioavailability. Bioavailability will be additionally assessed by Treatment Sequence. • Section 12.3: Subject as a random effect will be dropped from the MMRM

2 List of Abbreviations

Abbreviation	Definition
ACR	American College of Rheumatology
ADaM	Analysis data model
AE	Adverse event
AMS	Aseptic meningitis syndrome
ATC	Anatomical Therapeutic Chemical
AUC	Area under the curve
AUC _{0-last}	AUC from time point zero to the last quantifiable time point
AUC _{0-tau}	AUC from time point zero to tau
CDISC	Clinical Data Interchange Standards Consortium
CI	Confidence interval
CIDP	Chronic inflammatory demyelinating polyneuropathy
CM	Concomitant medication
C _{max}	Maximum concentration
CCI	CCI
C _{trough}	Trough concentration
DRM	Data review meeting
dcSSc	Diffuse cutaneous systemic sclerosis
CCI	CCI
ECG	Electrocardiogram
eCOA	Electronic clinical outcome assessment
eCRF	Electronic case report form
EOS	End of study
EULAR	European League Against Rheumatism
FAS	Full analysis set
CCI	CCI
CCI	CCI
HIV	Human immunodeficiency index
IgA	Immunoglobulin A
IgG	Immunoglobulin G
IP	Investigational product
IRT	Interactive response technology

Abbreviation	Definition
ISR	Infusion site reaction
ITP	Immune thrombocytopenic purpura
IV	Intravenous
lcSSc	Limited cutaneous systemic sclerosis
LLN	Lower limit of normal
CCI	CCI
MedDRA	Medical Dictionary for Regulatory Activities
CCI	CCI
PFT	Pulmonary function test
CCI	CCI
PID	Primary immunodeficiency
PK	Pharmacokinetics
SAE	Serious adverse event
SAF	Safety analysis set
SAP	Statistical analysis plan
SC	Subcutaneous
SD	Standard deviation
CCI	CCI
SMQ	Standardized MedDRA queries
SOC	System Organ Class
SSc	Systemic sclerosis
CCI	CCI
TEAE	Treatment-emergent adverse event
TEE	Thromboembolic event
CCI	CCI
ULN	Upper limit of normal
CCI	CCI

Glossary of Terms

Term	Definition
Baseline Value	The most recent assessment before the first infusion in Treatment Period 1.
End of Study (EOS)	The follow-up telephone call occurs 4 weeks after completing study treatment or early termination follow-up visit, whichever occurs later.
End of Treatment (EOT)	End of treatment is either end of Week 32 for completed subjects or at early termination visit.
Infusion	
IgPro10 An infusion comprises all IP exposure on one day of infusion. In the IgPro10 Treatment Periods, there are 2 to 5 consecutive days of infusions and so 2 to 5 Infusions planned per 4-week period.
 
IgPro20 An infusion comprises all IP exposure on one day (one session). In the IgPro20 Treatment Periods, there are 2 sessions and so 2 infusions planned per week.

Infusion Cycle (IgPro10 only)	One Infusion Cycle consists of 2, 3, 4 or 5 consecutive days of infusions with a planned total dose of 2 g/kg IgPro10 every 4 weeks. There are 4 planned Infusion Cycles of IgPro10 per IgPro10 Treatment Period in each Treatment Sequence.
Weekly Infusions (IgPro20 only)	A Weekly Infusion consists of 2 sessions (2 Infusions) with a planned total dose of 0.5 g/kg IgPro20 per week. There are 14 Weekly Infusions of IgPro20 per IgPro20 Treatment Period per each Treatment Sequence.
Infusion Session (IgPro20 only)	One Infusion Session consists of 1 infusion day. There are 2 Infusion Sessions within each weekly infusion with a planned total dose of 0.5 g/kg IgPro20 per week.
Protocol Deviation	
All instances when either subjects who have been entered in the study and / or the study sites deviate from the IEC / IRB-approved study protocol.
 
A key protocol deviation is any protocol deviation that could have a significant effect on the subject's safety, rights, or welfare and / or on the integrity of the study data.

Reference Visit	Reference visit for Treatment Period 1 is Week 1. Reference visit for Treatment Period 2 is Week 17.
Treatment Sequence	The study will consist of 2 Treatment Sequences, Treatment Sequence A or Treatment Sequence B. Each subject will be randomized to 1 of the 2 Treatment Sequences.

Term	Definition
Treatment Sequence A	IgPro20 0.5 g/kg/week subcutaneous (SC) infusion in Treatment Period 1 + IgPro10 2 g/kg/4 weeks intravenous (IV) infusion in Treatment Period 2.
Treatment Sequence B	IgPro10 2 g/kg/4 weeks IV infusion in Treatment Period 1 + IgPro20 0.5 g/kg/week SC infusion in Treatment Period 2.
Treatment	Treatment will be either IgPro20 0.5 g/kg/week or IgPro10 2 g/kg/4 weeks.

3 Purpose

This statistical analysis plan (SAP) provides a detailed and complete description of the planned statistical analyses for the final analysis of the study IgPro20_2001 to support the Clinical Study Report. Mock tables, listings, and figures shells are provided in separate supporting documents.

This SAP complies with the International Conference on Harmonisation (ICH) Harmonised Tripartite Guideline Topic E9, Statistical Principles for Clinical Trials. It is based upon the following study documents:

- Case Report Form (CRF), version 10 (27 Jul 2021)
- Clinical Study Protocol, Amendment 4 (22 Feb 2021)
- Data Transfer Specification Respiratory, version 3.0 (09 May 2019)
- Data Transfer Specification eCOA, version 1.0 (05 Jun 2019)
- Data Transfer Specification ICON lab services, version 7.0 (06 May 2020)
- Data Transfer Specification ECG, version 2.0 (01 Apr 2019)
- Data Transfer Specification PK, version 1.0 (02 Sep 2020)

All decisions regarding the final analysis of the study results, as defined in this SAP document, have been made prior to Database Lock of the study data.

The PK/PD and biomarker analysis will be described and reported outside the scope of this SAP (within a separate document/report).

4 Study Design

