8.1 Missing Data

8.1.1 Imputation of Non-Date Missing Data

Missing data occurs when any requested data is not provided, leading to blank fields on the collection instrument. These data will be indicated by the use of a “blank” in subject listing displays. Answers such as “Not applicable” and “Not evaluable” are not considered to be missing data and should be displayed as such.

Subjects with the designation of treatment relationship for AEs and SAEs missing will have the worst case assumed to impute the relationship: if relationship to study treatment is missing it will be assumed to be “Yes”. There will be no other imputation for missing data other than as described in Section 8.1.2 for partial dates and times.

In the event that the study is terminated, all available data will be listed and a review carried out by the study team to assess which statistical analyses are to be performed.

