8.2.4 Baseline Definition

Baseline is defined as the most recent, non-missing value prior to the start date and time of the first study treatment infusion. Results from unscheduled visits will be taken into account.

If date is given for an assessment only and the time is missing, and the date of the assessment is the same as the date of the first study treatment infusion then this assessment is NOT considered baseline.

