8.2.5 Change from Baseline or Reference Visit

Change from baseline will only be calculated for measures that have post-baseline records. Change from baseline is calculated as:

- Change from baseline = visit value – baseline value.

Percentage change from baseline is calculated as:

- Percentage change from baseline = $100 * \text{change from baseline} / \text{baseline value}$

If either the baseline or visit value is missing, the change from baseline and percentage change from baseline is set to missing as well.

The change from reference visit will be calculated following the same rules.

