8.2.6 Multiple Assessments

All data will be reported according to the nominal visit date for which it was reported (that is, no visit windows will be applied during data set creation to re-assign assessments to other visits or time points based on such windows).

Data from all assessments (scheduled and unscheduled), including multiple assessments, will be included in listings.

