11.4 Clinical Laboratory Evaluations

The laboratory tests in Section 8.1.1 of the protocol will be summarized as described in this section.

Laboratory data will be presented in units provided by the central laboratory.

Lab values will be summarized descriptively by visit using only values from scheduled visits.

Separate summary tables for hematology, biochemistry, and virology laboratory tests will be produced. Changes from reference visit and shift tables are produced for hematology and biochemistry only. For a list of laboratory tests see Clinical Study Protocol, Table 1.

The denominator in percentage calculation at a scheduled visit will be based on the number of subjects with a non-missing value at that visit.

The following summaries will be provided by groups defined in [Section 11](#):

- All laboratory values by visit
- Laboratory value changes from reference visit
- Laboratory value shifts from reference visit with respect to the normal range
- Summaries of potential clinically important values will be provided according to the categories in [Section 8.4.1](#).

Listings to be produced are:

- All Laboratory values, including changes from Baseline and Reference visit, values outside normal range will be flagged

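### Taken literally, the SAP's Period 1 reference visit (Week 1) leaves every Period 1 hematology and biochemistry change and shift empty, because those panels are drawn at Screening and not at Week 1

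*SAP*

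**What the plan says.** The SAP Glossary of Terms has separate entries for Baseline Value and Reference Visit. The second reads: "Reference visit for Treatment Period 1 is Week 1. Reference visit for Treatment Period 2 is Week 17". It names a visit and has no fallback to an earlier pre-infusion value. SAP Table 1 likewise starts Period 1 at Week 1.

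SAP 8.2.4 handles baseline differently: "Baseline is defined as the most recent, non-missing value prior to the start date and time of the first study treatment infusion". That rule would reach back to Screening.

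For laboratory data, SAP 11.4 says: "Changes from reference visit and shift tables are produced for hematology and biochemistry only". No separate summary of change from baseline is planned. The 11.4 listing covers both quantities: "All Laboratory values, including changes from Baseline and Reference visit, values outside normal range will be flagged".

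SAP 8.2.5 gives the missing-value rule, "If either the baseline or visit value is missing, the change from baseline and percentage change from baseline is set to missing as well", and extends it: "The change from reference visit will be calculated following the same rules".

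The protocol glossary defines the Period 1 reference visit as the study baseline, that is, the last assessment before the first Period 1 infusion. SAP section 5, which records departures from the protocol, does not mention the different wording.

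**The concern.** The laboratory change tables need a value at the reference visit, and the visit named for Period 1 has no laboratory draw. Change from baseline in clinical laboratory tests is a component of the IgPro20 primary endpoint (Protocol 2.1.2, SAP 4.2), and the reference-visit tables are the only tabulated laboratory change in the SAP.

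On the literal rule, the IgPro20 tables would contain only Sequence B, whose Week 17 reference value follows 16 weeks of IgPro10 with no washout. Sequence A, where IgPro20 is given without prior study IgPro10, would drop out. If this were found only in programming, the working definition for a primary-endpoint table would be settled outside the document meant to fix it.

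**Working it through.** The plan gives no figure to reproduce. The check compares the SAP rules with the schedules and then counts what can be computed.

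**Blood draws from Screening to the end of Period 1** (Schedules of Assessments for both sequences; Protocol 8.6.1, 8.6.2, 8.6.3, 8.6.5, and the Week 17 lists in 8.6.4.1 and 8.6.6.1)

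| Visit | Sequence A (IgPro20) | Sequence B (IgPro10) |
|---|---|---|
| Screening | hematology, chemistry, hemolysis, renal | hematology, chemistry, hemolysis, renal |
| Week 1, before infusion | PK only | PK only |
| Weeks 3, 7, 11, 15 | none of these panels | hemolysis and renal |
| Week 17, before first Period 2 infusion | all four | all four |

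The schedule tables and the visit-by-visit lists agree, so this does not come from a broken table.

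**Applying the SAP rules in order**

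1. Period 1 reference = Week 1 (glossary). Scheduled Week 1 hematology or chemistry values: 0 in Sequence A, 0 in Sequence B.
2. Change from reference = visit value − Week 1 value. With no Week 1 value, 8.2.5 makes the change missing; a shift from that visit has no starting category.
3. Screening results do not become Week 1 results under 8.2.6: "All data will be reported according to the nominal visit date for which it was reported", with no windowing to other visits. SAP 8.1.1 adds: "There will be no other imputation for missing data", apart from its rules for adverse-event relationship and partial dates.

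**Count**

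- Evaluable subjects: 10 + 10 = 20, giving 20 × 2 = 40 subject-periods.
- Period 1 subject-periods with no computable change: 10 on IgPro20 + 10 on IgPro10 = 20 of 40, or 10 of 20 for each product.
- If all of about 26 randomized subjects are infused: 26 / 2 = 13 per sequence, so about 13 + 13 = 26 subjects are affected.
- Period 1 change time points per completer: Sequence A has 1 (Week 17). Sequence B has 1 for the full panels (Week 17) and up to 4 + 1 = 5 for hemolysis and renal tests (Weeks 3, 7, 11, 15 and 17).
- Computable with Week 1 as reference: 0 in both sequences. Computable with the 8.2.4 baseline as reference: all of them, given a Screening value and the later sample.

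For Sequence A completers, Screening to Week 17 is the only scheduled laboratory change on IgPro20, so no partial result remains. Period 2 is computable because all four sets are drawn before infusion at Week 17.

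**What is not affected.** Vital signs, body weight and ECG are measured at Week 1, so Week 1 works as their reference. Observed laboratory values by visit, the summaries of potentially clinically important values (including creatinine against baseline) and the listed changes from baseline all remain.

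**The case against.** The strongest reply is that nobody would produce empty tables. The SAP is written against Protocol Amendment 4, whose glossary makes the Period 1 reference the study baseline. SAP section 5 lists departures as small as the wording of the trough definition, so its silence here suggests that Week 1 is shorthand rather than a change. Both terms must appear in 11.4 because they differ in Period 2, so listing both does not prove that they differ in Period 1. Only one pre-dose draw of these panels is scheduled, which leaves almost no analyst discretion. SAP 8.1.1 and 8.2.6 also carry limited weight, since using an observed Screening value as the comparator is neither imputation nor windowing. No hypothesis is tested.

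Much of this stands as evidence of intent, and it makes empty tables in the final report unlikely. It does not change what the rule says. The last-non-missing rule in 8.2.4 is written for baseline only, the glossary names a visit for the reference, and 8.2.5 and 11.4 then give missing changes. The protocol's definition was replaced in the SAP, not repeated. The case rests mainly on the glossary line together with 8.2.5 and 11.4, and that is sufficient.

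**Conclusion.** The concern holds on the literal wording. As written, the SAP gives no Period 1 laboratory change or shift in either sequence: 20 of 40 planned evaluable subject-periods, 10 of 20 for each product, including all Sequence A data on IgPro20.

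These counts assume 10 evaluable subjects per sequence, sampling as scheduled, and a glossary rule applied without correction. They describe what the rule produces, not a forecast of the final tables. Programmers would probably notice, and the mock shells, a separate document that was not available, may already use the right value. The point should be fixed because it concerns a component of the primary endpoint and the stated rule cannot be carried out. The underlying data are sound.

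**What to change.** - **SAP glossary, Reference Visit:** define the Period 1 reference value as the 8.2.4 baseline, the last non-missing value before the first infusion, including Screening. This restores agreement with the protocol glossary.
- **SAP 11.4:** state that the laboratory change and shift tables use this value. Note that for these panels it is normally the Screening result, taken up to 28 days before randomization. Say whether an unscheduled pre-infusion result may serve: 8.2.4 admits one, whereas 11.4 restricts summaries to scheduled visits.
- **Period 2:** no change is needed for this point. If the sponsor also aligns that wording with the protocol, it should carry the whole definition, including the condition that planned Period 1 treatment has been completed.
- **Table shells:** check that they match.

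The cost is a few lines of SAP text before database lock; the Screening data are already collected under the schedule. After lock, the choice would have to be reported as a deviation in the clinical study report, as SAP section 7 provides. The change restores the Sequence A IgPro20 laboratory comparison. It does not remove IgPro10 carry-over from Sequence B's Week 17 reference, which follows from a crossover without washout.

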4.1 Study Design

This is a prospective, multicenter, randomized, open-label, crossover study to investigate the safety and PK of IgPro20 and IgPro10 in patients with diffuse cutaneous systemic sclerosis (dcSSc). The PK portion of the study aims to evaluate the relative bioavailability of IgPro20, and characterize the PK of IgPro20 and IgPro10, respectively, in patients with dcSSc.

[figure not shown]
The study design is illustrated in [Figure 1](#). Patients with a diagnosis of dcSSc with disease duration ≤ 5 years and skin thickness scores of ≥ 15 to ≤ 45 as measured by **CCI** will be eligible to enroll in the study. All eligible subjects will be randomized (1:1) to Treatment Sequence A (IgPro20-IgPro10 Treatment Sequence) or Treatment Sequence B (IgPro10-IgPro20 Treatment Sequence). Each subject will complete Treatment Period 1 and Treatment Period 2 (16 weeks each), with up to 40 weeks (including Screening) of study duration for an individual subject.

In this crossover study, subjects in Treatment Sequence A will receive a total dose of 0.5 g/kg IgPro20 over 2 infusions per week every week in Treatment Period 1, and a total dose of 2 g/kg IgPro10 over 2 to 5 consecutive days every 4 weeks in Treatment Period 2. Subjects in Treatment Sequence B will receive a total dose of 2 g/kg IgPro10 over 2 to 5 consecutive days every 4 weeks in Treatment Period 1 and a total dose of 0.5 g/kg IgPro20 over 2 infusions per week every week in Treatment Period 2. Subjects weighing ≥ 100 kg will receive a fixed dose of 50 g IgPro20 every week, or 200 g IgPro10 every 4 weeks, respectively.

The dose of IgPro20 at 0.5 g/kg body weight weekly is equivalent to 2 g/kg body weight every 4 week dosing of IgPro10 if using 1:1 conversion and is the highest possible SC IgPro20 dose due to infusion volume limitation and potential safety concerns in subjects with SSs. As defined in the protocol, certain concomitant medications, below defined maximum doses, will be allowed for the treatment of dcSSc.

All subjects who complete the study or discontinue early will have a follow-up visit approximately 4 weeks after the last dose is administered.

Figure 1: Study Design

* Follow-up visit at the end of study approximately 4 weeks after the last dose administration

**EOT: The treatment period 2 stops at the end of Week 32

4.2 Objectives and Endpoints

Objectives	Endpoints
Primary	
To evaluate the safety of IgPro20 in adults with dcSSc	
 Number and percentage of subjects treatment-emergent AEs (TEAEs), serious AEs (SAEs), and AEs of special interest (AESIs) (total, by severity, by causal relationship) Number and percentage of subjects with AEs categorized as infusion site reactions (ISRs) (total, by severity, by causal relationship) Rate of ISRs per subject and per Infusion Onset and duration of ISRs Changes from baseline in vital signs and body weight, clinical laboratory tests, electrocardiogram (ECG), and pulmonary function tests (PFTs)

Objectives	Endpoints
Secondary	

To evaluate:
 
 • Relative bioavailability of IgPro20 • PK of IgPro20 • PK of IgPro10 • Safety of IgPro10 	
 • IgPro20 relative bioavailability (%F) • IgPro20 PK parameters (area under the curve [AUC]_{0-tau}, AUC_{0-last}, maximum [peak] plasma drug concentration [C_{max}], trough plasma drug concentration [C_{trough}]) • IgPro10 PK parameters (AUC_{0-tau}, AUC_{0-last}, C_{max}, C_{trough}) • The safety of IgPro10 based on: 
 ○ Number and percentage of subjects with TEAEs, SAEs, AESIs, and ISR (total, by severity, by causal relationship) ○ Changes from baseline in vital signs and body weight, clinical laboratory tests, ECG, and PFTs

CCI
 
 • CCI • • • • • • 	
 • CCI • • • • • •

4.3 Study Treatments

IgPro20 is a ready-to-use 20% liquid formulation of human IgG with > 98% IgG purity for SC administration, and is manufactured by CSL Behring (CSLB). IgPro20 is approved in the

United States of America (US), the European Union (EU), and other countries under the brand name Hizentra[®] for SC application in primary immune deficiency syndromes and other indications.

IgPro10 is a ready-to-use 10% liquid formulation of IgG with > 98% IgG purity for IV administration, and is manufactured by CSLB. The protein moiety of IgPro10 is approved in the US under the brand name Privigen[®] for the treatment of primary immunodeficiency (PID) in patients ≥ 3 years of age, for CIDP in adults, and for chronic immune thrombocytopenic purpura for patients ≥ 15 years of age. In addition, Privigen is approved for the treatment of CIDP in the adult and pediatric populations in the EU, Switzerland, Canada, and other countries.

